## Tegaderm™ Placement for Bag Mask Ventilation in the Bearded Patient

The data and statistics that would be required for a formal sample-size calculation with a reliable power estimate are not available. For that reason, the investigators plan a 2-phase process. In the first (external pilot) phase, the investigators plan to enroll 25 participants following a published guideline (Whitehead AL, et al. *Statistical Methods in Medical Research* 2016; 25:1057-73) and use the generated data to obtain effect-size and standard deviation information. Those statistics will permit a valid sample size calculation for the second phase, i.e. the main trial. The investigators will submit a modification to HRRC with sample size justification for the main trial prior to enrolling any patients for it.

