### 5. Number of Subjects

5.1. This is a single-site study.

5.2. The data that would be required for a formal sample-size calculation with a reliable power estimate are not available. For this reason, this study will use a 2-phase enrollment study plan with an initial 25-patient external pilot to inform the sample size calculation for the main phase. The investigators will submit a modification to HRRC with the planned sample size for the main phase upon completion of the

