## 7. Study Endpoints

7.1. *Describe the primary and secondary study endpoints.*

Primary outcome: Mask leakage, defined as the difference between average inspired and expired tidal volumes, as a percentage of inspired volume. Patients will serve as their own controls; the comparison is of the difference in leakage in the Tegaderm™ versus baseline conditions.

Secondary outcomes: 1. Difference in airway resistance between Tegaderm™ and baseline conditions, 2. Difference in peak inspiratory pressure between Tegaderm™ and baseline conditions, 3. Extent to which mask leakage change with Tegaderm™ depends on beard length.

7.2. *Describe any primary or secondary safety endpoints.*

If bag/mask ventilation is difficult and a Tegaderm™ not already in place, one will be placed in an effort to provide a better seal for the mask. If ventilation continues to be difficult, an Attending Anesthesiologist would attempt bag mask ventilation, consider placing an oral airway, and follow the difficult airway algorithm (6) by using supraglottic airway as a rescue device if deemed necessary. This event will be considered data and included in analyses.

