## Tegaderm™ Placement for Bag Mask Ventilation in the Bearded Patient

blockade to completion of one minute of mask ventilation with and without Tegaderm™ use. Patients will act as their own controls. Anesthesia induction and apnea will be defined as no voluntary respiratory effort and the absence of the eyelid reflex. Complete Neuromuscular blockade will be defined as Train of Four Ratio of **0/4** with neuromuscular monitoring at the *Corrugator Supercilii* muscle.

Once subjects are apneic and induced, **3** mask ventilation breaths will be administered in order to ‘acclimate’ the user to the mask and insure a proper thenar-eminence (TE) grip is being used. The randomized crossover trial will be started once complete neuromuscular blockade is verified. Every consecutive trial will alternate between starting with Tegaderm™ use and no alteration with patients acting as their own controls. Both no alteration and Tegaderm™ portion of exam will use the Resironics NM3™ (Resironics Deutschland, Herrsching, Germany) and CAPNOSTAT® 5 (Phillips Healthcare corporation, Eindhoven, The Netherlands) sensors to measure primary outcomes: Inspired tidal volumes (  $V_{t_{ins}}$ ; ml ), expired Tidal Volumes of End Tidal CO2 (  $V_{t_{Exp}}$ ; ml ) which will be used to determine predefined adequate BMV (Inspired Tidal Volume- Expired Tidal Volume difference of <15% defined as adequate) and secondary outcomes: within-patient differences between Tegaderm™ and no-alteration conditions for peak inspiratory pressures (  $PP_{ins}$ ; cm H2O ) and airway resistance (  $Res$ ; cm H2O/l/sec ) for 60 seconds, and facial hair grouping comparisons. The anesthesia machine will be set to deliver standardized pressure-controlled ventilation using common parameters: peak inspiratory pressure of 20 cm H2O, 10 breaths per minute, and an inspiratory-expiratory ratio of 1:2. These values are within common ranges used in standard practice, but may be modified during surgery as determined to be clinically appropriate by the attending anesthesiologist. General anesthesia will be maintained with sevoflurane 4-6% with 100% O2 at a rate of 6 liters per minute. Once data is gathered for the first part of the trial (no alteration or Tegaderm™), we will change our technique and collect data for second 60 seconds component of the trial in similar fashion to initial data collection.

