## 13. Data Analysis

13.1. *Describe the data analysis plan, including any statistical procedures.*

Paired data (within patient differences in leakage,  $PP_{ins}$ , and airway resistance) will be assessed with paired t-test or Wilcoxon rank-sum test, depending on distribution normality. Beard condition groups will be compared on the primary outcome (leakage difference  $> 15\%$  significant) with ANOVA or Kruskal-Wallis test, also depending on distribution normality. Sensitivity analysis will provide percentage of observed standard deviation for detection of leakage difference and a traditional power analysis to provide the sample size required to detect significant outcome with our intervention.

13.2. *Provide a power analysis, if applicable*

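### Section 13.2 names the effect size, as well as the SD, from 25 pilot patients as the basis for the main-trial sample size, and no target difference, alpha, sidedness or power is stated

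*Combined protocol and SAP*

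**What the plan says.** Section 13.2 explains that the inputs for a formal sample-size calculation do not exist, so a 25-patient external pilot comes first. The investigators will "use the generated data to obtain effect-size and standard deviation information", and "Those statistics will permit a valid sample size calculation for the second phase". Section 5.2 is softer: it describes an "initial 25-patient external pilot to inform the sample size calculation for the main phase".

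Section 13.1 promises "a traditional power analysis to provide the sample size required to detect significant outcome with our intervention" but names no difference to detect. The same sentence mentions a "percentage of observed standard deviation for detection of leakage difference", which refers to the observed SD and sets no target either.

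The primary outcome in 7.1 is "the difference between average inspired and expired tidal volumes, as a percentage of inspired volume", compared within patient between Tegaderm and baseline. A 15% figure appears twice. In 12.1 it defines adequate ventilation within one condition ("Expired Tidal Volume difference of <15% defined as adequate"). In 13.1 it is a bracketed remark in the sentence beginning "Beard condition groups will be compared on the primary outcome". Neither is tied to sizing the Tegaderm-versus-baseline comparison.

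On timing, 13.2 has the sample-size modification submitted before any main-phase patient is enrolled. Section 5.2 lets main-phase enrolment start as soon as the pilot ends, with at most 25 main-phase patients before HRRC authorises the modification.

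**The concern.** A sample size needs a difference to detect, an SD, an alpha and a power. The plan offers only pilot estimates for the first two and nothing for the others. An SD from 25 pairs is usable. A mean difference from 25 pairs carries a standard error of 0.2 SD (1/√25), which is large beside any plausible effect.

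If that estimate becomes the target, N follows the pilot's luck. A fortunate pilot produces a main trial that is too small, and an unfortunate one a trial far larger than needed. At stake are a main trial that may miss a real benefit and, in the other direction, patients enrolled without need.

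**Working it through.** The plan gives no main-trial N, so there is no figure of its own to reproduce.

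**Inputs from the documents.** 25 pilot patients (5.2, 13.2), each measured under both conditions (7.1), so 25 within-patient differences and 24 df. Paired t-test (13.1; its rank-test alternative is not modelled).

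**Assumed, because the plan is silent.** Normal differences, two-sided 0.05, 80% target power (90% as a sensitivity check), and a true effect δ, in SDs of the within-patient difference, of 0.3, 0.5, 0.8 or 1.0.

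**Step 1, correct N.** Power(N, δ) = P(|T| > t with 0.975 and N−1 df), where T is noncentral t with N−1 df and noncentrality δ√N. The smallest N reaching 80% is 90, 34, 15 and 10 for the four effects.

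**Step 2, spread of the pilot estimate.** With d = pilot mean/SD, 5d is noncentral t with 24 df and noncentrality 5δ. At δ = 0.5 the 10th and 90th percentiles of d are 0.24 and 0.80. Sizing on these gives N = 136 and N = 15. True power at N = 15 is 44%, against 81% at the correct 34.

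**Step 3, chance that true power is below 60%.** At δ = 0.5, N = 21 gives 59% and N = 22 gives 61%, so the trial falls below 60% when N is 21 or fewer. That happens when d is at least 0.643. P(T > 5 × 0.643 = 3.21; 24 df, noncentrality 2.5) = 26.9%. The same steps for each effect:

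| True effect (SD) | Correct N | Largest N with power <60% | P(power <60%), sized on observed effect | Power at N = 25 |
|---|---|---|---|---|
| 0.3 | 90 | 56 | 35.6% | 30% |
| 0.5 | 34 | 21 | 26.9% | 67% |
| 0.8 | 15 | 9 | 15.5% | 97% |
| 1.0 | 10 | 6 | 7.0% | 99.8% |

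With a 90% target, the chance at 0.3 and 0.5 SD is 25.8% and 14.9%. An uncorrected normal-approximation N gives somewhat worse figures at the 80% target (36.6% and 31.6%), so the table is the milder version.

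**Step 4, oversizing.** N exceeds twice the correct value in 31.8% of pilots at 0.3 SD (above 180) and 22.0% at 0.5 SD (above 68).

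**Step 5, fixed target with only the SD from the pilot.** Here 24s²/σ² is chi-square with 24 df. At 0.5 SD, N is 21 or fewer when s/σ ≤ 0.5/0.643 = 0.778, so P(chi-square ≤ 24 × 0.778² = 14.5) = 6.6%. At 0.3 SD the result is 7.6%. With a 90% target both are about 1%.

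**Step 6, limits of the fixed target.** If the target is 25% above the true effect, the 0.5 SD condition becomes s/σ ≤ 0.625/0.643 = 0.972. The chance of power below 60% is then 46.2% (49.4% at 0.3 SD). Using the upper one-sided 80% confidence limit of the SD multiplies s by √(24 / 20th percentile of chi-square with 24 df) = 1.15. The chances then fall to 15.5% and 17.3%.

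**The case against.** **The plan does not state the rule that does the harm.** A reader might infer that the investigators have committed to using the observed effect unchanged. The documents do not go that far: 13.2 names it as an input, and 5.2 says only that the pilot informs the calculation. This stands, and the figures above are conditional on it. What remains is that 13.2 names the pilot effect size as an input and the plan supplies no other target.

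**Large effects.** A reader might also infer that the risk matters across the whole range of effects. It does not. At 0.8 and 1.0 SD, power below 60% needs a main trial of at most 9 or 6 patients, while 5.2 and 5.3 already seek authority for 25 main-phase patients. Although 25 is a cap before authorisation and not a floor, so small a main trial is unlikely. Section 9.3 mentions recruiting 60 patients in a year. If that is the total (an assumption), 35 would remain for the main phase, giving 82% power at 0.5 SD but only 41% at 0.3 SD.

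**HRRC will review the modification.** True, and the target could be set there. But the plan gives HRRC nothing else to size against, and a difference chosen once the pilot effect is known can be fitted to it. Because the pilot is external, this does not by itself inflate the main trial's type I error, and no such claim is made.

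**A fixed target can be wrong too.** This also stands. With a target 25% too high, the fixed-target approach without the SD limit does worse on this measure than sizing on the observed effect (46% against 27% at 0.5 SD).

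**The 15% remark in 13.1 might be a relevance threshold.** It could be developed into one, but it sits in the beard-group comparison and is not presented as a sizing target.

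**Conclusion.** The concern holds in a limited form. Section 13.2 makes the pilot effect size a basis for the main-trial N and calls the calculation valid, while no section states a target difference, alpha, sidedness or power for it.

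If the observed effect is used as the target, N depends heavily on chance at small to moderate effects. At 0.5 SD it runs from about 15 to about 136 against a correct 34, and about 27% of pilots lead to true power below 60% (about 36% at 0.3 SD). These sizes rest on the assumed paired t-test, normal differences, two-sided 0.05 and 80% target. At 0.8 SD or more the practical weight is small, since 25 main-phase patients would give at least 97% power.

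The documents do not show that an error has already been made, nor would a pre-set target guarantee power. This is a change that should be made before the pilot is analysed, held with medium confidence. The conflict between 5.2 and 13.2 on when main-phase enrolment may begin is separate and needs no assumptions.

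**What to change.** In 13.2, before the pilot is analysed, state and justify the smallest Tegaderm-versus-baseline difference in percent leakage, on the 7.1 scale, worth detecting. Give alpha, sidedness and power with it. Take only the SD of the within-patient differences from the pilot.

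The investigators must choose the difference. Fifteen percentage points is only a candidate: it would need N of 16, 34 or 58 if that SD were 20, 30 or 40 points (assumed SDs; two-sided 0.05, 80% power).

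Optionally, use the upper one-sided 80% confidence limit of the pilot SD (1.15 times the estimate). This guards against a low pilot SD and softens the effect of a target set too high.

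Separately, reconcile 5.2 with 13.2 on whether the modification is submitted before the first main-phase patient is enrolled.

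The cost is protocol wording and possibly a larger N. A smaller target raises N, and the SD limit makes it about one third larger (1.153² = 1.33; median 43 instead of 33 at 0.5 SD with an 80% target).

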### **14. Provisions to Monitor the Data to Ensure the Safety of Subjects**

*This section is required when research involves more than Minimal Risk to subjects. Describe:*

- 14.1. The PI will perform data and safety monitoring every 2 months, but the PI works closely with all study team members and will be kept apprised of study progress, including any adverse events.
- 14.2. The PI will review the collected data and the Electronic Anesthesia Record which already includes relevant safety outcomes and patient participant EMR. Relevant data includes oxygenation and ventilation parameters, airway pressures, and other information relevant to airway management. The data will be reviewed for desaturation events, elevated airway pressures, and any other adverse clinical outcomes related to airway management during the study. Any such adverse events would be immediately apparent in the stated records. The PI will obtain statistical advice as appropriate, but adverse events are expected to be sufficiently uncommon that they are likely to be addressed on a case-by-case basis.
- 14.3. The PI will refer to the EMR as appropriate to obtain relevant context on any adverse events.
- 14.4. Mask ventilations are routine prior to intubation and safety profiles are well established. It is not anticipated that the medical literature will report new findings that call the safety of this study into question.
- 14.5. The PI will review the incidence of adverse events related to Tegaderm™ use in this study to determine whether they exceed the incidence that would be expected without the use of the intervention. If, in the PI's opinion, adverse events occur and are related to the study, the PI will suspend the study and notify HRRC as noted in 14.6 below.
- 14.6. In accordance with HRRC policy, the PI will suspend the study in the event of any adverse outcome that is both significant and likely due to the procedure under investigation, in the PI's opinion, and report the event to HRRC for its review and subsequent recommendation.
- 14.7. The PI will notify HRRC in the event of study termination under 14.6 above.

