## 6. Study Timelines

6.1. Describe time expectations:

Individual patients' participation will last less than five minutes.

Investigators anticipate that 12 to 18 months will be sufficient to enroll the planned 2-phase sample size.

Study completion (analysis and preparation of manuscripts and other presentations) is expected to take approximately 12 months after enrollment is completed.

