## Tegaderm™ Placement for Bag Mask Ventilation in the Bearded Patient

abort or proceed with the protocol. In the event of a cardiac event or equivalent the protocol will be aborted and the patient will be excluded from the trial.

12.2. Study data will be derived from the research interaction with the patient, and the electronic medical record (EMR). These data will be recorded on a data collection form that will be deidentified and associated with a unique study code. Data to be collected are as follows.

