## **16. Data Management/Confidentiality**

- 16.1. Most members of the research team are physicians who interact with these and similarly-situated patients on a daily basis.
- 16.2. The research does require the use of direct identifiers (e.g. MRN) in order to accurately obtain complication data and link it to procedural data.
- 16.3. The research requires the use of Private Health Information (PHI), but the investigators will not disclose any identifiable information except as required by law.
- 16.4. The data do not include information that is typically considered to be sensitive, such as HIV status, substance abuse, or criminal behavior.
- 16.5. The investigators do not plan to pursue a Certificate of Confidentiality.
- 16.6. All investigators have completed routine UNM Health Sciences Center (HSC) training on the secure management and use of patient data. Identifiable data on paper forms will be maintained in a locked cabinet in a study team member's Anesthesiology Department office, which is a patient-restricted area; and in electronic format will be stored on HSC secure servers, which are password-protected.
- 16.7. Data will be deidentified upon completion of data collection and entry into a spreadsheet stored on UNM HSC secure servers, but will be identifiable (via a linking document containing study ID numbers and MRNs) until that point in order to permit accurate linkage of procedural and outcome data.

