## 18.Risks to Subjects

- 18.1. The only identified risks are of allergy to the Tegaderm™ adhesive, which is rare; and mild irritation, which is uncommon. The risk of bag mask ventilation causing aspiration of stomach contents and barotrauma are theoretical and highly unlikely in this study population. The risk of these events occurring do not increase with our protocol (addition of 2 minutes of bag mask ventilation) versus an elective general anesthetic as we have excluded all patients that would incur this added risk. All research involves risks of loss of confidentiality, inconvenience, stress, and emotional upset.
- 18.2. The risk of allergic reaction is mitigated by performance of study procedures in UNMH operating rooms, which are furnished with the personnel, facilities, equipment, and supplies necessary to respond to any such eventuality. It is also mitigated by exclusion of patients with known allergy to the product. Risks associated with multiple iterations of bag/mask ventilation are mitigated by the presence of attending anesthesiologists, who are experts in all aspects of airway management. The remaining listed risks are mitigated by adherence to procedures as described in this document as well as routine HRRC policies/procedures.
- 18.3. The investigators have not identified any aspects of this study that may carry unforeseeable additional substantial risks.

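### Section 14.5 promises to review the incidence of dressing-related adverse events, but no skin or allergy assessment is planned to supply the count

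*Combined protocol and SAP*

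**What the plan says.** All references are to the combined protocol and SAP.

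- **Risks (18.1).** "The only identified risks are of allergy to the Tegaderm™ adhesive, which is rare; and mild irritation, which is uncommon". No rates are given. Aspiration and barotrauma are mentioned as theoretical.
- **Commitment (14.5).** "The PI will review the incidence of adverse events related to Tegaderm™ use in this study", in order "to determine whether they exceed the incidence that would be expected without the use of the intervention". No expected incidence is stated.
- **Targets of the record review (14.2).** "The data will be reviewed for desaturation events, elevated airway pressures, and any other adverse clinical outcomes related to airway management during the study". The sources are the collected data, the electronic anesthesia record and the EMR. The section adds that such events would show at once in those records.
- **General reporting (14.1).** The PI works closely with the team and "will be kept apprised of study progress, including any adverse events".
- **EMR (14.3).** It is consulted for context on adverse events.
- **Data list (12.2).** "Data to be collected are as follows" introduces patient background items, then provider level, paralytic, beard length, randomization result and respiratory parameters.
- **Safety endpoints (7.2).** The text covers difficult ventilation and rescue.
- **Identifiers (16.2).** They are kept "in order to accurately obtain complication data and link it to procedural data", but no complication is listed or defined.

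**The concern.** An incidence needs a count of events among patients who were all assessed in the same way. The protocol names two skin or allergic risks and promises to look at their frequency, yet no listed data item, endpoint or scheduled check would record them. The patient is under general anesthesia while the dressing is on and cannot report itching or soreness. A mild reaction enters the EMR only if someone happens to look and chart it.

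What is at stake is the meaning of a low or zero count. Without a planned look, zero recorded skin events could mean that none occurred or that none were noted, and the 14.5 review could not tell these apart. The same would apply to any sentence in the report about harm from the dressing.

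**Working it through.** The plan states no safety rate or safety sample-size figure, so there is nothing of its own to reproduce. The check has two parts.

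**1. Does any planned item capture the named risks?**

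| Section | What it covers | Skin or allergy item |
|---|---|---|
| 18.1 | Identified risks | Both named |
| 14.5 | Incidence review of dressing-related events | Covered in principle; no method given |
| 14.1 | Any adverse event, by team reporting | Covered only if someone notices and reports |
| 14.2 | Desaturation, airway pressure, airway-management outcomes | None named |
| 7.2 | Difficult ventilation and rescue | None |
| 12.2 | Background, provider, beard, randomization, respiratory items | None |
| 16.2 | Complication data through the record number | Not defined |

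The commitment exists, but the collection that would serve it does not. No section schedules a skin check, says when the dressing is removed in relation to intubation, or sets an observation period for skin events.

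The comparison in 14.5 has a further gap. In this crossover every patient who completes both periods wears the dressing. The trial therefore has no unexposed group in which to observe the incidence expected without it, and no outside figure is stated.

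**2. What could a zero count show?**

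Inputs: n = 25 (pilot) and n = 50 (initial authorization), from 5.2 and 5.3, taking every enrolled patient as exposed. The documents describe the risks only as rare and uncommon, so the true rates p of 1%, 2%, 5% and 10% are assumptions. The captured fraction s is also an assumption: 1 for full capture and 0.5 for half.

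Exact (Clopper-Pearson) two-sided 95% upper limit for zero events with full capture, 1 − 0.025^(1/n):

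- n = 25: 1 − 0.025^(1/25) = 13.7%
- n = 50: 1 − 0.025^(1/50) = 7.1%

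If only a fraction s of events is recorded, these limits apply to s × p, so the limit on p is divided by s. At s = 0.5:

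- n = 25: 0.1372 / 0.5 = 27.4%
- n = 50: 0.0711 / 0.5 = 14.2%

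Chance of at least one recorded event, 1 − (1 − s × p)^n:

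| Assumed p | n = 25, s = 1 | n = 25, s = 0.5 | n = 50, s = 1 | n = 50, s = 0.5 |
|---|---|---|---|---|
| 1% | 22.2% | 11.8% | 39.5% | 22.2% |
| 2% | 39.7% | 22.2% | 63.6% | 39.5% |
| 5% | 72.3% | 46.9% | 92.3% | 71.8% |
| 10% | 92.8% | 72.3% | 99.5% | 92.3% |

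For example, at p = 5% and n = 25, full capture gives 1 − 0.95^25 = 72.3% and half capture gives 1 − 0.975^25 = 46.9%. With half capture, a pilot with a true 5% rate would more often than not record nothing (100% − 46.9% = 53.1%). The plan gives no basis for any particular s, so these figures show scale and do not estimate what will be missed.

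**The case against.** The strongest reply is that section 14 is not confined to airway events. The team reporting in 14.1, the dressing-event review in 14.5 and the suspension provision in 14.6 all reach beyond the airway. That is correct. An overt allergic reaction in a monitored operating room could reach the anesthesia record, the EMR or the PI directly. A reader might infer that the safety review looks only at the airway, or that the named risks would go wholly uncounted. The documents do not support either.

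Three further inferences also fail.

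- **A five-minute safety window.** Section 6.1 says "Individual patients' participation will last less than five minutes", and 14.2 speaks of events during the study. Section 6.1 gives a participation time. Section 14 does not adopt it as an observation window, and its record review has no time cut-off.
- **Aspiration and barotrauma missed.** Both fall within the airway-management outcomes that 14.2 already covers.
- **Suspension cannot operate.** Suspension under 14.5 turns on the PI's opinion that events occurred and were related. Section 14.6 can act on a single significant outcome. Neither needs a rate.

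It is also fair that the dressing is used during 60 seconds of mask ventilation (section 21), that known allergy is an exclusion, that no tolerability conclusion is planned, and that the guideline hope in 2.3 concerns effectiveness. The data form and the consent form were not available for this review, so an unlisted field or an instruction to patients cannot be ruled out.

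These points limit the consequence. They do not supply a skin assessment or a numerator for 14.5.

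**Conclusion.** The point holds as a gap between a commitment and its data. Section 14.5 promises an incidence review of dressing-related events, and 18.1 names two such risks, but neither the listed data nor any scheduled check would record them systematically. Mild irritation is the event likely to be under-counted; overt allergy is less exposed to this.

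In size, zero events could be read as excluding rates above 13.7% (n = 25) or 7.1% (n = 50) only if every exposed patient was checked. At an assumed half capture, the limits are 27.4% and 14.2%. The true rates and the captured fraction are assumptions.

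The efficacy endpoints are unaffected, and the ability to suspend for a recognized reaction remains. The change is worth making because it is cheap and lets the 14.5 review do what it promises.

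**What to change.** - **12.2.2:** add a skin and allergic-reaction field, completed when the dressing is removed and again at the routine recovery-room check. Record explicitly when nothing is found, so that a zero can be told from a missing check. The protocol does not say when removal occurs in relation to intubation, so the form should note the time of the check.
- **14.2:** name adhesive and skin reactions among the events reviewed, with one observation period from dressing placement to recovery-room discharge. Make clear that the statement about events showing at once in the records applies to airway events only.
- **14.5:** report the number of patients with a skin or allergic event over the number exposed and checked, with an exact 95% interval. Alternatively, state the reference rate that the comparison uses and its source.

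The cost is a few form fields, a brief look by staff already present, and minor extra charting. Redness from the mask or from tube tape may be counted as a dressing event. The check at removal limits this where the dressing comes off before the tube is taped. None of this changes treatment or the efficacy analysis.
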